5. PATIENT ELIGIBILITY AND CRITERIA

The target study population comprises patients with metastatic lung cancer who are eligible for an immunotherapy agent as monotherapy or combination therapy.

5.1 Inclusion Criteria

1. Histologically or cytologically confirmed Stage IV NSCLC according to the 7th AJCC staging manual. Patients with recurrent disease after definitive treatment with surgery or concurrent chemoradiation are eligible.
2. Patients must be eligible for an immunotherapy agent as determined by treating medical oncologist. Patients who progress after drug therapy (3 months) for ALK, EGFR or ROS mutation positive lung cancer are eligible. Patients who received prior combination immunotherapy or single agent monotherapy are eligible. Patients who progress on maintenance immunotherapy are eligible if sites of progression are amenable to local therapy for control.
3. At least 2 lesions that are safely amenable to SBRT/SABR.
4. ECOG ≥ 2 .
5. At least 1 measurable lesion according to Response Evaluation Criteria in Solid Tumors (RECIST) 1.1 criteria for response assessment or at least 1 lesion with FDG avidity and CT correlate that can be monitored for PET-CT response by SUV Max increase or decrease.
6. ≥ 18 years old.
7. Normal Hepatic and renal function.
8. Bone marrow reserve:
 - a. ANC $\geq 1.5 \times 10^9/L$
 - b. Hemoglobin ≥ 9.0 g/dL
 - c. Platelet count $\geq 75 \times 10^9/L$
9. Ability to comply with follow-up visits and evaluations, treatment planning and studies and other study related procedures and visits.
10. Ability to sign informed consent.

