2.0 PROPOSED TRIAL RATIONALE

Anti-PD-1 antibodies have demonstrated activity in the treatment of lung cancer. Opdivo was approved in February of 2015 by the FDA for patients with metastatic squamous NSCLC with progression on or after platinum based therapy. In the open-label trial, patients were randomized to receive OPDIVO (n=135) administered at 3mg/kg every 2 weeks. Median survival was improved to 9.2 months compared to 6 months in patients receiving docetaxel (n=137) 75mg/m² every 3 weeks, p=0.00025. Median progression free survival was slightly improved to 3.5 months compared to 2.8 months but 1 year overall survival was improved to 42% compared to 24% (36).

We expect that improvements in local control, increased immunogenic response and abscopal effect seen with combined modality treatment will result in improved local control, progression free survival and resultant significant increases in overall survival beyond 3 months. We propose a pilot/phase II study to assess the safety and efficacy of combination immunotherapy and stereotactic ablative radiation therapy (I-SABR).

Treatment will be a sequential combination treatment of SABR/SBRT and immunotherapy to assess the safety and feasibility of treatment. SABR/SBRT will be administered in 3-5 daily treatments followed by immunotherapy following the conclusion of SABR/SBRT. This approach will take advantage of the transient increase in antigen availability, increased antigen presentation and upregulation of PD-1 by tumor cells following ablative radiation therapy. After an interim safety analysis, the study will continue to the phase II portion where overall survival, progression free survival and response rate will be the primary and secondary end points. For reference, outcomes will be compared to the immunotherapy arms of checkmate 057 and Keynote 042 trials.

Several trials examining combination I-SABR are currently underway. A table of selected studies is included in [Table 1](#).

Study (Institution)	SABR Target	Dose (Gy/Fractionation)	Immunotherapy Agent	Sequence
NCT02239900 (MD Anderson Cancer Center)	Liver Lung Adrenal	50/4 60/10	Ipilimumab	Concurrent/Sequential
NCT01862900 (Chiles Research Institute)	Lung Liver	15/1 201/1	Anti-OX40	Concurrent
NCT01769222 (Stanford University)	Any	20/2	Ipilimumab	Concurrent
NCT02298946 (NIH/NCI)	Liver	8/1 24/3	PD-1 Inhibitor	Sequential

Table 1. List of selected ongoing I-SABR studies

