5.3 Sample Size

More than 350 patients with metastatic lung cancer present to the Crozer-Keystone health system for treatment annually. If 50% of patients are eligible for this study, we expect approximately 100 patients will enroll and be treated on this study. Patients will be followed for 2 years on the study. The study will conclude 2 years after the last patient is enrolled. An interim safety and feasibility analysis will be performed on the first 20 patients in the pilot phase. Overall survival, progression free survival, local control and subgroup analysis will be performed on the entire patient cohort at the conclusion of the study.

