8.2 Data Collection

Patients will be stratified by number of metastatic lesions. ≤ 3 lesions, 4-5 lesions and ≥ 5 lesions.

All study data will be coded and de-identified. Codes and patient data will be stored separately in a password protected file. Any hard copies will be stored in a locked file cabinet. All other data will be stored on a password secured and encrypted computer only accessible to study staff.

Adverse event data collection and reporting, which are required as part of every clinical trial, are done to ensure the safety of patients enrolled in the studies as well as those who will enroll in future studies using similar agents. Adverse events are reported in a routine manner at scheduled times during the trial by the study investigator.

For pre-specified time points and required reporting please see Appendix IV.

APPENDIX I. RECOMMENDED DOSE MODIFICATION OR DISCONTINUATION AND SUPPORTIVE CARE GUIDELINES FOR SPECIFIC DRUG-RELATED ADVERSE EVENTS

Event(s)	CTCAE v4.03 Grade	Management	Action/Supportive Care Guidelines	Symptoms ^a	Differential Diagnosis

Colitis events
 
 • Bowel obstruction • Colitis • Colitis microscopic 	
≤ Grade 1
	
No change in dose
	
For diarrhea, treat symptomatically (loperamide, oral hydration, electrolyte substitution and ADA colitis diet). Endoscopy is recommended if symptoms persist.
 
 • Grade 1 diarrhea that persist for >1 week should be treated with the addition of oral diphenoxylate hydrochloride and atropine sulfate four times daily and budesonide 9 mg daily. 	
Symptoms may include (but are not limited to):
 
 • Abdominal pain, cramping and/or bloating 	
All attempts should be made to rule out other causes such as metastatic disease, bacterial or parasitic infection, viral gastroenteritis, or the first manifestation of an inflammatory bowel disease by examination for stool leukocytes, stool cultures, and a Clostridium difficile titer.

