APPENDIX III: STUDY PARAMETERS AND ASSESSMENTS

Table 5.0: Pre-treatment assessments

Assessment	Time Points
	≤ 30 days prior to registration
Evaluation by a radiation oncologist	X
Evaluation by a medical oncologist	X
History/physical examination	X
Performance Status (ECOG)	X
CBC w/ diff & ANC, platelets, ALT, AST	≤ 30 days prior to registration.
Serum/urine pregnancy test (if applicable)	≤ 14 days prior to registration
CT Scans of the chest/abdomen/pelvis with radionuclide bone scan OR whole body PET/CT	X
Histological confirmation from at least one metastasis	x
MRI of the vertebral column	If vertebral column metastases identified on staging and will be treated

Table 6.0: Post-Treatment Assessments**ASSESSMENTS IN FOLLOW-UP**

Assessment	Time Points	
	30 days after completion of SBRT	Every 3 months after completion of SBRT for a total of 2 years
Physical examination	X	X
Evaluation by a radiation oncologist	X	X
Performance status	X	X
ALT, AST, Total and Direct Bilirubin	X (If SBRT delivered to the liver)	X (If SBRT delivered to the liver) Perform at 3 months then every 6 months
Hgb	Recommended if clinical symptoms of anemia on physical exam post-treatment	
Diagnostic Imaging		X Per protocol or if clinically warranted
Adverse event evaluation	X	X

LIST OF COMMON ABBREVIATIONS AND DEFINITIONS OF TERMS

ADL	Activities of Daily Living
AE	Adverse event
AESI	Adverse event of special interest
ALP	Alkaline phosphatase
ALT	Alanine aminotransferase
ANA	Antinuclear antibody
ANC	Absolute neutrophil count
aPTT	Activated partial thromboplastin time
ARGUS	Pharmacovigilance and clinical safety software system
AST	Aspartate aminotransferase
AUC	Area under the concentration–time curve
BAL	Bronchoalveolar lavage
BC	Breast cancer
BUN	Blood urea nitrogen
CPA	Cyclophosphamide
CR	Complete response
CRF; eCRF	Case report form (electronic or paper); electronic case report form
CRO	Contract research organization
CRP	C-reactive protein
CT	Computed tomography
CTLA-4	Cytotoxic T-lymphocyte antigen 4
CTV	Clinical target volume
(NCI-) CTCAE	(National Cancer Institute) Common Terminology Criteria for Adverse Events
DLT	Dose-limiting toxicity

Dmax Maximum radiation dose

EC Ethics committee

ECG Electrocardiogram

EDC Electronic data capture

FDG-PET 18F-fluorodeoxyglucose positron emission tomography

FFPE Formalin-fixed, paraffin-embedded

FNA Fine-needle aspirate

fx Fraction(s)

GCP Good clinical practice

GBM Glioblastoma multiforme

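### Inclusion item 4 requires ECOG 2 or higher: as printed it bars every ECOG 0–1 patient, sets no upper limit, and appears reversed

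*Protocol*

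**What the plan says.** Section 5.1 lists ten inclusion criteria. Item 4 and the start of item 5 read: "4. ECOG ≥ 2 . 5. At least 1 measurable lesion according to Response Evaluation Criteria in Solid Tumors (RECIST) 1.1". The two copies of the revised inclusion criteria in Addendum 2 (section 1.1) repeat item 4 unchanged.

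Performance status otherwise appears only in the assessment tables of Appendix III. Table 5.0 lists "Performance Status (ECOG") among the assessments due within 30 days before registration, and Table 6.0 repeats performance status in follow-up. Neither table gives a range. The exclusion criteria, in section 5.2 and in both addendum copies, do not mention it.

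Section 5 describes the intended population broadly: "The target study population comprises patients with metastatic lung cancer who are eligible for an immunotherapy agent as monotherapy or combination therapy".

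**The concern.** Higher ECOG grades mean worse function, so a lower bound of 2 with no upper bound selects patients with impaired performance and turns away the fittest. Nothing in the rationale, the hypothesis or the description of the target population asks for that.

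The criterion is operative, because ECOG must be recorded before every registration. It therefore decides who enters two things:

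- **The pilot.** Section 5.3 states: "An interim safety and feasibility analysis will be performed on the first 20 patients in the pilot phase". Under section 3.1, the pneumonitis rate in these patients decides whether lung-directed treatment stays permitted in phase II.
- **The single-arm survival cohort.** Section 2.0 states: "For reference, outcomes will be compared to the immunotherapy arms of checkmate 057 and Keynote 042 trials". With no concurrent control, the meaning of that comparison depends on a clearly defined population.

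**Working it through.** The question is one of wording, and the protocol has no figure to reproduce. The check sets the relevant passages side by side.

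**1. What the printed rule admits.** Take grades 0–4 of the standard scale.
- Printed rule, ECOG ≥ 2: admits {2, 3, 4} and bars {0, 1}.
- The same number with the sign turned, shown only to measure the gap: admits {0, 1, 2} and bars {3, 4}.
- The two readings share grade 2 alone. Which way staff read the line therefore changes eligibility for four of the five grades.

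**2. Whether another passage supplies the limit.**

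| Place | What it says on performance status |
|---|---|
| Section 5, target population | No restriction |
| Section 5.1, item 4 | ECOG ≥ 2 |
| Section 5.2, exclusions | Nothing |
| Addendum 2, section 1.1, item 4 (two copies) | ECOG ≥ 2 |
| Addendum 2, section 1.2, exclusions (two copies) | Nothing |
| Appendix III, Tables 5.0 and 6.0 | To be assessed; no range |

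The addendum revised the eligibility list, and its item 2 differs slightly from item 2 of section 5.1. Item 4 was left alone, so no current text corrects it. The addendum copies are one text repeated and do not independently confirm the sign.

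**3. Whether the rest of the list fits a population with impaired performance.** Item 7 requires normal liver and kidney function, item 8 sets marrow reserve, and item 9 asks for "Ability to comply with follow-up visits and evaluations, treatment planning and studies and other study related procedures and visits". These select for fitness. None of them explains a bar on ECOG 0–1.

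**4. Whether the sign could be a PDF misreading.** It is the same in all three places. In the same list, ≥ makes sense for age and for the blood counts. Table 5.0 prints ≤ for its 30-day and 14-day windows, so the two signs are kept apart in the text. A misreading is unlikely.

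**5. Accrual.** Section 5.3 gives more than 350 patients a year, which over two years is 350 × 2 = 700. Its conditional 50% leaves 350, and 100/350 = 28.6%. The protocol gives no ECOG distribution. If 20–40% were ECOG 2 or higher (an assumption):
- of 700: 0.20 × 700 = 140 to 0.40 × 700 = 280;
- of 350: 0.20 × 350 = 70 to 0.40 × 350 = 140.

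Whether 100 patients could be reached depends on the assumed share and on the base chosen. No accrual failure is claimed.

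**The case against.** The best reply is that this is an obvious slip in a trial run by one health system under one principal investigator, and that staff will know what was meant. Other items also limit the practical risk. Item 2 states: "Patients must be eligible for an immunotherapy agent as determined by treating medical oncologist". Items 9 and 10 require ability to comply and to consent, so free entry of ECOG 3–4 patients is less likely than the bare wording suggests. That part stands. But none of these items is a performance-status limit, and none relieves the bar on ECOG 0–1. Nor can staff derive the intended ceiling, because the protocol never states one.

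Two further cautions are fair. The protocol does not give the performance-status criteria of the external trials, so no mismatch with them can be shown, and it calls that comparison one for reference. Nor does any passage link performance status to pneumonitis. No size or direction of bias can therefore be claimed for survival or toxicity. What remains is that item 4 determines who is in the pilot and in the cohort.

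The stratification line in section 8.2, "Patients will be stratified by number of metastatic lesions. ≤ 3 lesions, 4-5 lesions and ≥ 5 lesions", is poor evidence that signs were read correctly, since its strata overlap at 5. The case against a misreading rests instead on the three identical copies and on the sensible use of both signs elsewhere.

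**Conclusion.** The point holds and must be fixed. As written, item 4 bars two of the five grades 0–4 (0 and 1) and does not bar the other three. It governs all 100 planned patients, including the 20 in the pilot, and no current text corrects it.

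The printed wording and the missing upper limit are certain. That the sign is reversed is a well-supported inference, since the intended range is nowhere stated. Either way of proceeding fails: followed literally, the trial studies only patients with impaired performance; read as a ceiling, each ECOG 0–1 enrolment departs from the written criteria. The consequences for survival, toxicity and accrual cannot be sized from this document.

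**What to change.** The sponsor and investigator should confirm the intended ECOG range and issue a correcting amendment. It should restate item 4 with the confirmed direction and an explicit upper limit, in identical words in section 5.1 and in both copies of Addendum 2, section 1.1. The limit itself is for them to state; none is proposed here. Patients already enrolled should be checked against the confirmed range, using the ECOG values required before registration, and any deviation recorded.

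The cost is one line in three places plus a review of data the protocol already requires. Sample size and analysis do not change.

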5.2 Exclusion Criteria

1. Patients with active CNS metastases. If metastases are treated and patients return to baseline and no steroids are required, patients are eligible.

2. Active, known or suspected auto-immune disease.
3. Patients with medical conditions that require systemic immunosuppression.
4. Patients with a history of interstitial lung disease.
5. Other active malignancy requiring intervention.
6. Prior lung radiation, with the only metastatic targets in the lungs.
7. Unresolved toxicity from prior chemotherapy or anti-cancer treatment.
8. Current or prior enrollment in clinical trial with an investigational drug within 4 weeks.
9. Pregnancy or positive pregnancy test.

5.3 Sample Size

More than 350 patients with metastatic lung cancer present to the Crozer-Keystone health system for treatment annually. If 50% of patients are eligible for this study, we expect approximately 100 patients will enroll and be treated on this study. Patients will be followed for 2 years on the study. The study will conclude 2 years after the last patient is enrolled. An interim safety and feasibility analysis will be performed on the first 20 patients in the pilot phase. Overall survival, progression free survival, local control and subgroup analysis will be performed on the entire patient cohort at the conclusion of the study.

5.4 Discontinuation of Study Treatment

Patients who discontinue study treatment will be asked to return to the clinic for all remaining study visits per the visit schedule, and will be expected to continue with relevant study assessments.

5.5 Withdrawal from Study

During the treatment period and follow-up period, a patient who withdraws consent to continue participation in the study will be removed from follow-up requirements. Routine clinical care will continue but no data will be collected for study purposes.

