3. STUDY OBJECTIVES

3.1 Primary Objectives

The primary objective of the pilot phase of the study is to characterize the safety, feasibility and tolerability of sequential combination I-SABR in patients with metastatic NSCLC. The first 20 patients will be evaluated for 15 weeks following treatments with I-SABR prior to continuing enrollment. In the Brahmer trial, 5% of patients in the Nivolumab arm developed pneumonitis with a median time to onset of treatment related pulmonary events of 15 weeks. All but one patient with pulmonary events were treated with glucocorticoids and all cases resolved with a median time to resolution of 5 weeks (range 0.6-12.1 weeks).

If more than 5% of patients develop grade ≥ 3 pneumonitis during the initial evaluation phase, no lung directed therapy will be permitted during the phase II portion.

The primary objective of the phase II portion of the study will be overall survival.

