4.1 STUDY DESIGN AND DURATION

This is a combination single arm pilot/Phase II study of combination I-SABR for metastatic NSCLC. Treatment safety and feasibility will be assessed in the initial pilot phase and oncologic outcomes will be assessed in the second phase.

After screening, patients will receive 3-5 fractions of SBRT/SABR to up to 3 metastatic sites in addition to the primary tumor. Following the conclusion of SBRT/SABR, patients will receive Immunotherapy therapy at standard dosing until disease progression or discontinuation of treatment due to toxicity or patient choice (Figure 1).

Tumor assessment will be performed prior to SABR initiation and every 3 months or for clinical disease progression.

Figure 1: Sample Patient Treatment and Follow-Up Timeline

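### Section 5.5 stops all data collection, vital status included, when consent is withdrawn; if withdrawal is related to prognosis, the primary OS estimate may be biased, probably upward

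*Protocol*

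**What the plan says.** Section 3.1 of the protocol sets the endpoint: "The primary objective of the phase II portion of the study will be overall survival". Section 4.1 fixes the design: "This is a combination single arm pilot/Phase II study of combination I-SABR for metastatic NSCLC". Section 2.0 names the reference: "outcomes will be compared to the immunotherapy arms of checkmate 057 and Keynote 042 trials".

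Two adjacent sections govern patients who leave:

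- Section 5.4, stopping treatment: "Patients who discontinue study treatment will be asked to return to the clinic for all remaining study visits per the visit schedule". These patients stay in survival follow-up.
- Section 5.5, withdrawing consent: "a patient who withdraws consent to continue participation in the study will be removed from follow-up requirements", and then "Routine clinical care will continue but no data will be collected for study purposes".

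Section 5.5 makes no exception for survival status and does not mention public death records. The visits that section 5.4 asks for are set out in Appendix III, Table 6.0: physical examination and radiation-oncology evaluation at 30 days and then three-monthly for two years.

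On size and duration, section 5.3 says "we expect approximately 100 patients will enroll and be treated on this study" and "Patients will be followed for 2 years on the study". No expected withdrawal rate appears anywhere in the protocol.

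**The concern.** The rule in section 5.5 is explicit, so it is more than a detail left open for the analysis plan: an analysis cannot use deaths that the protocol says will not be collected. It also sits at one end of a two-step scale. A patient either keeps attending clinic or leaves the dataset altogether. A patient too unwell or unwilling to travel every three months, who would not object to a record check, has no other exit described. Section 5.5 itself says that routine care goes on, so the date of death may be in the medical record and still be unusable.

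Kaplan-Meier estimation treats a censored patient as having the same future risk as those still followed. If patients who withdraw are doing worse than those who stay, OS is overstated; if they are doing better, it is understated. In a randomised trial some of this could be common to both arms. Here there is one arm, and any distortion goes straight into the figure that is read against outside results.

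**Working it through.** **Plan's own figure.** There is none to reproduce. The 100 patients are an accrual expectation, and section 5.3 gives no power, target effect or dropout rate.

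**Inputs from the protocol.** OS median of 9.2 months and 1-year OS of 42% on nivolumab (section 2.0); about 100 patients and 24 months of follow-up (section 5.3). The 9.2 months comes from the squamous nivolumab trial, which is not one of the two named comparators, and serves only as a scale. Exponential survival with that median gives 1-year OS of 0.5^(12/9.2) = 40.5%, close to the quoted 42%, so a constant hazard is adequate for illustration.

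**Assumptions (not in the protocol).** Share withdrawing consent within 24 months, p = 2%, 5%, 10% or 20%; death hazard after withdrawal, k times the on-study hazard, k = 0.5, 1, 2, 3 or 5.

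**Model.** On-study death hazard λ, withdrawal hazard g, post-withdrawal hazard kλ, per month.

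1. Share observed to withdraw, with death competing: p = g/(g+λ) × [1 − exp(−24(g+λ))].
2. True survival, counting deaths after withdrawal: S(t) = exp(−(λ+g)t) + g/(λ+g−kλ) × [exp(−kλt) − exp(−(λ+g)t)].
3. Choose λ and g so that step 1 gives p and S(9.2) = 0.5.
4. With censoring at withdrawal, Kaplan-Meier estimates exp(−λt), so the reported median is ln 2/λ.

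**Example, p = 10%, k = 2.** The solution is λ = 0.07280, g = 0.00956.

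- Step 1: 0.00956/0.08236 × [1 − exp(−1.977)] = 0.1161 × 0.8615 = 0.100.
- Step 2: S(9.2) = 0.4687 + 0.0313 = 0.500.
- Step 4: 0.6931/0.07280 = 9.52 months, a bias of +0.32.

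**Reported median (months) when the true median is 9.2, with bias in brackets:**

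| Withdrawal | k = 0.5 | k = 1 | k = 2 | k = 3 | k = 5 |
|---|---|---|---|---|---|
| 2% | 9.16 (−0.04) | 9.20 (0) | 9.26 (+0.06) | 9.30 (+0.10) | 9.35 (+0.15) |
| 5% | 9.09 (−0.11) | 9.20 (0) | 9.36 (+0.16) | 9.46 (+0.26) | 9.58 (+0.38) |
| 10% | 8.97 (−0.23) | 9.20 (0) | 9.52 (+0.32) | 9.73 (+0.53) | 9.98 (+0.78) |
| 20% | 8.71 (−0.49) | 9.20 (0) | 9.88 (+0.68) | 10.33 (+1.13) | 10.88 (+1.68) |

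**Cross-check.** A simulation of 1,000,000 patients that instead fixes the on-study median at 9.2 months gives +0.31 months at 10% and k = 2, +0.62 at 10% and k = 4, +1.21 at 20% and k = 4, and −0.53 at 20% and k = 0.5. The pattern is the same.

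**Sampling error for scale.** With 100 patients, expected deaths by 24 months are 100 × [1 − 0.5^(24/9.2)] ≈ 84. The 95% interval for a 9.2-month median is 9.2 × exp(±1.96/√83.6), about 7.4 to 11.4 months.

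**The case against.** Ending data collection when consent is withdrawn is an ordinary protection for participants and is not an error. That stands; the point is only that the protocol offers no intermediate choice.

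Section 5.4 keeps patients who stop treatment in follow-up, including those who stop for toxicity or progression, among whom decline would be expected to concentrate. That also stands: it narrows the problem to consent withdrawal and makes low withdrawal rates credible. At 2-5% the bias is at most about 0.4 months in this model, small beside an interval of 7.4 to 11.4 months. Sampling error is, however, shown in the interval, and this bias is not.

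The consent pages and the SAP are not at hand. A graded choice could be in the consent form, but it would then conflict with the unqualified wording of section 5.5. Rules for censoring belong in the SAP, but they cannot bring back deaths that were never collected.

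A reader might infer that OS is biased upward as a matter of fact, and biased against the historical arms. The protocol supports neither. It says nothing about the prognosis of patients who withdraw: the bias is nil if withdrawal is unrelated to prognosis and negative if withdrawers do better. It also does not say how CheckMate 057 or Keynote 042 handled withdrawal; if they censored in the same way, part of the distortion would offset. Nor should the bias be measured against a 3-month gain. Section 2.0 mentions 3 months only as a general expectation, and the protocol sets no such design target.

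**Conclusion.** The point holds in a limited form. Section 5.5 ends collection of vital status at consent withdrawal, in a single-arm study whose primary phase II endpoint is OS, and no status lies between full visits and complete cessation. This creates an opportunity for informative censoring; it does not show that any will occur. An upward direction is the more likely one in metastatic NSCLC, but that is a judgement and not something the protocol documents.

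Across the assumed 2-20% withdrawal and hazard ratios of 0.5 to 5, the bias in median OS runs from about −0.5 to +1.7 months. The upper end needs 20% full withdrawal of consent and a fivefold hazard together. All of these figures rest on constant hazards, an illustrative 9.2-month median, and withdrawal rates and hazard ratios that are assumed. The rule is worth changing because the change is cheap and protects the primary endpoint, not because a large bias has been demonstrated.

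**What to change.** Amend section 5.5, with matching consent wording, to offer graded withdrawal. A patient may leave study visits and assessments while agreeing to passive survival follow-up. For patients who do not explicitly refuse it, the site records date of death or date last known alive from medical and public records, and these dates enter the OS analysis. An explicit refusal still stops all collection. Recording which form of withdrawal each patient chose would let the report state how many were lost to OS and when.

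The cost is a small IRB and consent amendment and some record checking, with no added visits. The change has to be made prospectively: without consent to passive follow-up, deaths after withdrawal may not be usable later.
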